Spasmodic dysphonia (SD) is a task-specific primary focal dystonia characterized by selective loss of voluntary voice control during speech production due to uncontrolled spasms in the laryngeal muscles. SD is a chronic debilitating condition, which often extends beyond vocal communication impairment and causes significant occupational disability and life-long social isolation. SD becomes even more incapacitating when it is associated with voice tremor (VT), characterized by rhythmic alterations in pitch and loudness during vowel production and by inability to sustain a vowel for more than a few seconds. Action-induced VT, which is present in about 1/3 of SD patients, often resembles SD symptoms, complicating the differential diagnosis and treatment of these disorders. At present, SD and VT are diagnosed using their voice and speech characteristics, while the outcome of “gold standard” treatment with botulinum toxin injections into the laryngeal muscles helps confirm the initial diagnosis. However, response to botulinum toxin does not reliably separate SD and VT. Moreover, it cannot be used for successful treatment of all SD and VT patients because it is mostly beneficial for the adductor type of SD (ADSD), but not for the abductor type (ABSD) or VT. Current limitations in the clinical management of SD and VT stem from our limited understanding of the pathophysiology underlying these disorders and the lack of biomarkers for their diagnosis and treatment. There is, therefore, a critical need to determine the neural correlates contributing to the pathophysiology of SD and VT in order to establish disorder-specific biomarkers and to elucidate the mechanism of action of alternative treatment options in these patients.

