1.3.1 Study #1: Mapping disorder-specific brain activation in patients with SD vs. SD/VT using fMRI during symptomatic voice and speech production. We will use a sparse-sampling event-related BOLD fMRI design on a 3.0 Tesla Philips MRI scanner. We already successfully used this design for the investigations of voice and other laryngeal behaviors (Loucks et al., 2007; [name] et al., 2007; [name] et al., 2009; [name] and Ludlow, 2010). Brain activity will be studied during production of 10 symptomatic speech sentences (e.g., "We eat eels every day", "Sam has a rabbit in his hand") and syllables (repetitive vowel /i/ and continuous vowel /i/). In the scanner, subjects will listen to an auditory example of the task presented in a pseudorandomized order and reproduce it within the 5-s interval of the 'silent' period of scanning, only after which a 2-s image acquisition will follow, while the subjects remain silent and motionless. A resting condition without auditory presentation will serve as a baseline. Four scanning sessions will be acquired with a total of 36 experimental trials and 24 baseline conditions. Structural MRI will be acquired for an anatomical reference.

Data analysis will follow the similar processing pipeline as previously employed by us using AFNI software ([name] et al., 2007; [name] et al., 2009; [name] and Ludlow, 2010). Following initial data processing, the task-related responses will be analyzed using multiple linear regression with a single regressor for each task convolved with a canonical hemodynamic response function. Baseline drifts will be modeled using quadratic polynomials in time for each separate imaging run, and motion parameter estimates will be used as additional regressors of no interest in the multiple regression analysis. To account for disorder-specific vocal motor differences between SD and SD/VT groups, such as adductor and abductor voice breaks and shakiness, respectively, we will include the number of voice breaks and severity of voice tremor as variables in a within-group statistical analysis. Quantitative measures of SD and VT symptoms will be derived from the *Study 1.3.3* within this Aim. The correction of individual statistical parametric maps for multiple comparisons will be performed using Monte-Carlo simulations (Forman et al., 1995), which will identify a minimum cluster size at a voxelwise threshold of 0.005 at overall significance level of a corrected $p \leq 0.025$.

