Study population and Sample size. To estimate the number of subjects in this study, we reviewed our recent DTI studies, which used a similar experimental design to examine white matter abnormalities in SD patients and controls ([name] et al., 2008; [name] et al., 2009). Significantly decreased FA was found in the right genu of the internal capsule in SD (patients vs. controls: 0.55 ± 0.05 vs. 0.61 ± 0.07). Using these values, a power of 80% at a 0.025 significance level will be obtained with 18 subjects per group for the proposed study based. Again, to increase the statistical significance and allow for between-study comparisons, we propose to recruit the same 20 subjects per SD, SD/VT and control group for the DTI study. The statistical power for tractography is the same.

1.3.4 Study #4: Relationship between brain abnormalities and clinico-behavioral characteristics in SD and SD/VT.

The role of neuroimaging studies in elucidation of pathophysiological mechanisms of SD would be considerably enhanced if coupled with strategies that yield information about their relevance to symptom elicitation. Additionally, identification of disorder-specific brain abnormalities that are correlated with disorder symptoms can prove useful for assessment of efficacy of existing and newly developed therapeutic interventions. Our approach here will be to examine the relationships of functional brain activity and structural brain organization with clinico-behavioral correlates (i.e., disorder severity scores). For all 20 subjects per group (both patients and controls), the behavioral measures will be obtained during initial intake screening, history and physical examination, and three-tiered diagnostic questionnaire (see *Appendices 1 and 2*). Patients' voice and speech will be digitally recorded during scanning for offline acoustic analysis to assess the SD and VT severity.

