All recruited subjects will be outpatient. To establish their eligibility for participation, *all* subjects will be first screened through the administration of the intake screening questionnaire, which will contain general questions about their health. SD patients will additionally be questioned about their disorder (e.g., onset, site, treatment, effects of alcohol of voice symptoms) (see **Appendix 1**).

Diagnosis of SD will be established based on the three-tiered approach as follows:

- (i) *the patients' self-screening questionnaire*, which will include questions regarding the amount of the effort required for speaking (e.g., Does it take a lot of work for you to talk?) and the presence of symptoms during different vocal activities (e.g., Can you do any of the following normally? Shout, Cry, Laugh, Whisper, Sing, Yawn) (**Appendix 2, Tier 1**);
- (ii) *voice and speech recording and evaluation*, which will include the acoustic analysis of 20 adductor sentences with a high number of glottal stops and vowels and 20 abductor sentences with a high number of voiceless consonants (/p/, /t/, /k/, /s/, /h/, /f/) produced in normal speaking voice and in a whisper (**Appendix 2, Tier 2**);
- (iii) *detailed laryngological examination*, which will include fiberoptic nasolaryngoscopy to observe the presence of vocal fold spasms during voice and speech production (**Appendix 2, Tier 3**);
- (iv) *detailed neurological examination*, which will be performed to exclude other neurological conditions, especially other forms of dystonia and tremor (**Appendix 2, Tier 3**).

Diagnosis of VT in SD will be established based on the following additional criteria:

- (i) Vocal tremor during vocalization that primarily involves laryngeal structures;
- (ii) Exclusion of other laryngeal pathologies based on fiberoptic nasolaryngoscopic examination.

We have successfully used this approach of subject selection in our previous studies. Furthermore, a recent pilot study of 30 patients with SD, VT and muscle tension dysphonia found 97% accuracy in the classification of these disorders using the above-described three-tiered approach.

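### Study 1.3.1 models neither how long nor when each subject speaks before the single 2-s image, so shorter continuous /i/ in SD/VT could be read as lower activation

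*Combined protocol and SAP*

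**What the plan says.** Section 1.3.1 (Study #1) uses sparse sampling. Subjects hear an example and "reproduce it within the 5-s interval of the 'silent' period of scanning, only after which a 2-s image acquisition will follow". The tasks are "production of 10 symptomatic speech sentences" and "syllables (repetitive vowel /i/ and continuous vowel /i/)". There are 36 task trials and 24 baseline trials; the split of the 36 by task is not given.

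The first-level model is "multiple linear regression with a single regressor for each task convolved with a canonical hemodynamic response function", with polynomial drift and motion estimates as the only other terms. Voice-break counts and tremor severity are brought in to allow for vocal motor differences, but in a within-group analysis. The between-group ANOVA in the same section has subject as random and task and group as fixed factors, with no performance term.

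Specific Aims characterizes voice tremor partly "by inability to sustain a vowel for more than a few seconds". The criterion that assigns patients to SD/VT (Protection of Human Subjects, section 1a) is "Vocal tremor during vocalization that primarily involves laryngeal structures", together with exclusion of other laryngeal pathology. It has no duration rule.

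Section 1.3.4 says patients' "voice and speech will be digitally recorded during scanning for offline acoustic analysis to assess the SD and VT severity". Recording of controls is not mentioned there, although the Facilities section describes a scanner audio system that records voice. Section 2.3.1 reuses the first-level model for the scans before and after sodium oxybate and records voice at both.

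**The concern.** With one short image per trial at a fixed time, the sampled signal depends on the neural response and also on when speech began and how long it lasted. If one group phonates for less time, its image is lower even when its neural activity while speaking is the same. The group contrast cannot separate the two.

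Continuous /i/ is the task on which the plan's own description of voice tremor leads one to expect a difference between SD/VT and the other groups. The voice-break and tremor variables do not close the gap: they are not listed in the between-group model, and neither measures onset or duration.

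What is at stake is the SD versus SD/VT contrast, the purpose of Aim 1. The PPI and DCM analyses use task time series from the same scans and would carry the same ambiguity. The before-versus-after drug contrast uses the same model, so a change in speech timing between scans would likewise be read as a change in activation.

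**Working it through.** **The plan's own figure.** Section 1.3.1 plans on 0.63 ± 0.16 (SD) versus 0.39 ± 0.23 (controls) percent signal change, two-tailed alpha 0.025, 80% power.

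- Difference: 0.63 − 0.39 = 0.24.
- Pooled s.d.: √((0.16² + 0.23²)/2) = 0.198.
- Standardised difference: 0.24/0.198 = 1.21.
- The noncentral t calculation gives 14.3, so 15 per group. The stated 15 reproduces. At the 20 to be recruited, power is 0.93.

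**Effect of duration on the sampled signal.** Speech is a boxcar from onset to end, convolved with a response function and averaged over the image at 5–7 s. Neural activity while speaking is held equal. Two response shapes were tried: a double gamma (shapes 6 and 16, ratio 1/6) and a single gamma. Onset is at 0, and phonation for the full 5 s is set to 1.00. All durations are assumptions.

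| Phonation | Double gamma | Single gamma | Loss (double gamma) |
|---|---|---|---|
| 4 s | 0.96 | 0.98 | 4% |
| 3 s | 0.83 | 0.87 | 17% |
| 2 s | 0.60 | 0.63 | 40% |

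If hearing the example uses the first 1.5 s of the window (also an assumption), the reference is phonation from 1.5 to 5 s. Then 2 s of phonation gives 0.83–0.89, a loss of 11–17%.

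**What this does to SD versus SD/VT.** Suppose both groups truly sit at 0.63, with s.d. 0.198, 20 per group and alpha 0.025 in a single region. With signal factor f in SD/VT, the spurious difference is 0.63 × (1 − f), and the t-test noncentrality is (difference/0.198) × √(20/2).

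- f = 0.96: difference 0.025, noncentrality 0.40, declared significant about 4% of the time.
- f = 0.83: difference 0.107, noncentrality 1.71, about 28%.
- f = 0.60: difference 0.252, noncentrality 4.02, about 95%. This is as large as the planned 0.24.

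These are for a contrast on the vowel alone. If the vowel is one third of an averaged task effect (assumed), f = 0.60 gives 0.252/3 = 0.084, declared significant about 17% of the time. At f = 0.80 the figure is 0.126/3 = 0.042 and about 6%.

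**Direction.** Every factor is below 1, so shorter phonation lowers the SD/VT signal. At f = 0.39/0.63 = 0.62, a true SD/VT level of 0.63 would fall to the control mean and the abnormality would disappear from view.

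**The case against.** **A few seconds may fill the window.** The window is at most 5 s, so the limit on sustaining a vowel may cost little, and Protection Against Risk reports that patients usually have no trouble performing the tasks in the scanner. This stands as a limit on size: at 3 s or more of prompt phonation the loss is at most about 17%. A reader might infer that SD/VT patients by definition cannot do the task. The documents do not say so; the limit is a described characteristic, and the diagnostic criteria contain no duration rule.

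**The limit concerns a sustained vowel in voice tremor.** It says nothing about sentences or repetitive /i/, about SD without tremor, or about late onset. This stands. The documented basis is continuous /i/ in SD/VT.

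**The bias runs against the hypothesis.** This stands too. A reader might set a 40% loss beside the planning difference, (0.63 − 0.39)/0.63 = 38%, and infer that timing could explain it. It cannot: that contrast is SD versus controls, with patients higher, whereas shorter phonation makes the affected group lower.

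**A drug effect could be an artefact.** A reader might also infer this. Longer phonation after symptom relief would raise the signal, against the expected attenuation; later onset would lower it. Section 2.2.1 lists dose-dependent sedation, but nothing in the documents shows that speech timing changes.

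**One regressor per task does not exclude trial-specific event lengths.** Correct. The plan is silent on timing; it does not state a fixed interval.

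**Shortened phonation is itself a symptom.** Adjusting for it may remove part of what the study wants to map. This is a reason to show both analyses, not a reason to leave timing unmeasured.

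**Conclusion.** The concern holds for continuous /i/ in SD/VT patients. The stated first-level and group models have no term for utterance onset or duration, the plan's own account of voice tremor gives reason to expect shorter phonation on that task, and the variables meant to allow for vocal differences are within-group and do not measure timing.

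The size is a signal loss of about 4%, 17% or 40% for 4, 3 or 2 s of phonation against 5 s. This rests on assumed durations, prompt onset, a canonical response and an image at 5–7 s. It shrinks if listening takes part of the window or if the vowel is averaged with other tasks. The likely consequence is false SD/VT hypoactivation, or masking of the hypothesised hyperactivation. The documents do not support a claim of false hyperactivation, nor a firm claim about the other tasks or the drug comparison, where a timing difference is possible but not documented. This is a worthwhile and cheap improvement, not a defect that invalidates the study.

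**What to change.** - Score the onset and duration of each utterance from the in-scanner recordings.
- Record controls as well as patients, using the existing scanner audio system.
- Tabulate onset and duration by group, task and session.
- Repeat the SD versus SD/VT, patient versus control and before-versus-after contrasts with regressors built by convolving the response function with each trial's actual speech interval, at least for continuous /i/. Report them beside the planned analysis.
- State in section 1.3.1 what event onset and length the planned regressors use, and whether listening falls inside the 5-s window.

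The cost is scoring time, recording for controls and one further first-level model. The timing-adjusted contrast answers a slightly different question, because shortened phonation belongs to the disorder. Both results should therefore be shown, with the reading agreed beforehand: if timing is balanced they should agree; if they differ, the timing table shows why.

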1.3 Research Design

The following 3 groups of subjects will participate in all proposed studies of the Specific Aim #1: (1) SD patients; (2) SD/VT patients, and (3) healthy controls, who have no history of any neurological, psychiatric or laryngological problems. Because SD is a rare disorder, both ADSD and ABSD patients will be included to closely match with ADSD/VT and ABSD/VT patients, which will ensure the homogeneity between patient populations. Based on the reported SD clinical prevalence (Ludlow et al., 2008) and our own experience, we estimate that about 80% of the participating patients will have ADSD and 20% will have ABSD. SD patients only with VT without ET in other body parts will be recruited. Because the majority of VT patients report improvement of their voice symptoms after alcohol intake, we predict that at least 60% of recruited SD/VT group will also be ethanol-responsive. To further assure homogeneity between patient populations, we will carefully match SD and SD/VT patients according to their report of alcohol effects, in addition to their age, gender and an SD type match. Eligibility of patients will be established based on a three-tiered approach, including initial screening interview, detailed voice/speech, laryngological and neurological examinations (see *Appendices 1 and 2*), as previously described (Ludlow et al., 2008). Any subject with neurological (other than SD and SD/VT), psychiatric, or laryngological problem will be excluded from the study. All recruited patients must be symptomatic; if they are treated with botulinum toxin injections, they may be included only if they are symptomatic, that is at the end of their botulinum toxin treatment cycle. Controls will be carefully matched with SD and

SD/VT populations by their age and gender. Although we have a large neuroimaging database of SD patients and controls, those data were acquired by the PI on a different MRI scanner several years ago and, therefore, will not be used in the proposed studies to ensure the consistency in the scanner use and study design.

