For group analysis, the 3-D anatomical datasets of each subject will be spatially normalized and converted to the standard anatomical space. The resulting normalization parameters will be applied to the 4-D time series datasets. To estimate the main effect of a task per group, the group analysis will be carried out using a three-way analysis of variance (ANOVA) with subject as a random factor and the task and group as fixed factors ($p \leq 0.025$, voxelwise corrected) to identify (1) shared abnormalities in all patients vs. controls, and (2) distinct abnormalities between SD vs. SD/VT patients. Statistical differences in brain activation extent will be assessed using the subtraction method within the three-way ANOVA design. This univariate data analysis will provide information about the extent and intensity of brain activation in different groups (i.e., SD and SD/VT patients vs. controls and SD patients vs. SD/VT patients).

To further our knowledge of functional brain abnormalities in SD and VT, we will perform multi-stage brain network analysis, which will allow for identification of abnormal brain networks and the relationship between the key network regions, possibly contributing to the pathophysiology of these disorders. For this, we will first perform a correlation analysis between functional and structural datasets in SD and SD/VT patients to determine the brain regions of abnormal function with underlying structural changes. The structural data will be derived from the *Studies 1.3.2 and 1.3.3*.

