Data analysis. Similar to our recent study in SD ([name] and Ludlow, 2011), brain volume in each subject will be segmented into gray matter, white matter, and CSF. VBM analysis will follow the standard procedure using VBM8 toolbox in the SPM8 software. Spatial normalization will be performed using a diffeomorphic nonlinear registration tool (DARTEL) to improve inter-subject registration (Ashburner, 2007). Voxelwise statistical differences in GMV between groups will be examined using independent t -tests with age, gender, total intracranial volume, number of SD-specific voice breaks, severity of tremor and disorder duration as nuisance effects (Ashburner and Friston, 2000). The cluster-level significance will be assessed using a conservative non-stationary cluster extent correction (Hayasaka and Nichols, 2004) at $p \leq 0.025$.

Study population and Sample size. The same 3 groups of SD, SD/VT and healthy control subjects recruited for the fMRI study will participate in this study. To determine the sample size for this study, we reviewed our previous study in 40 SD patients and 40 controls ([name] and Ludlow, 2011). That study found increased GMV in the laryngeal primary sensorimotor cortex (HV vs. SD: 0.22 ± 0.04 vs. 0.26 ± 0.04). Using these values, t -test indicated that a sample size of 17 subjects per group will provide 80% power to detect group differ-

ences at a 0.025 significance level in the present study. To increase statistical power of the proposed studies and account for subjects' dropout possibilities, we will recruit the same 20 subjects per group, who participate in the 1.3.1. *Study #1*.

1.3.3 Study #3: Mapping disorder-specific white matter abnormalities in patients with SD vs. SD/VT using DTI.

In this study, we propose to identify white matter abnormalities contributing to SD and SD/VT using DTI on a 3.0 Tesla Philips scanner. Whole-brain brain images will be acquired using spin-echo EPI sequence with paired gradient pulses for diffusion weighting; diffusion will be measured along at least 33 non-collinear directions. We successfully used a similar scanning protocol in our previous studies ([name] et al., 2008; [name] et al., 2009).

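### The fMRI plan says voice breaks and tremor account for vocal differences between SD and SD/VT, but the SD vs. SD/VT contrast as written carries neither measure

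*Combined protocol and SAP*

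**What the plan says.** All references are to the combined protocol and SAP.

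- **Purpose (1.3.1 Study #1, data analysis).** The voice measures are brought in "To account for disorder-specific vocal motor differences between SD and SD/VT groups".
- **Means (same sentence).** "we will include the number of voice breaks and severity of voice tremor as variables in a within-group statistical analysis".
- **Model for the group comparison (1.3.1, group analysis).** A "three-way analysis of variance (ANOVA) with subject as a random factor and the task and group as fixed factors". One of its two listed products is "distinct abnormalities between SD vs. SD/VT patients".
- **How the difference is formed (1.3.1).** "Statistical differences in brain activation extent will be assessed using the subtraction method within the three-way ANOVA design". No voice measure is named in this model.
- **Matching (1.3 Research Design).** SD and SD/VT patients are matched "according to their report of alcohol effects, in addition to their age, gender and an SD type match". Symptom severity is not a matching factor.
- **Gray matter comparison (1.3.2 Study #2).** Here the between-group tests do carry the "number of SD-specific voice breaks, severity of tremor and disorder duration as nuisance effects", along with age, gender and intracranial volume.

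**The concern.** The stated aim concerns a difference between two groups; the stated method works inside each group. Unless the voice variables are carried into the SD vs. SD/VT contrast, they explain scatter among patients of the same group and leave the contrast as it was.

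The scans are taken while patients produce speech chosen to bring out symptoms, so activation may depend on how many breaks occur. If one patient group breaks more often in the scanner, some of the difference between the maps may follow from that. Section 1.4 expects Aim 1 to yield markers useful for differential diagnosis. A region that tracks break frequency supports that use less well than one that separates the groups at equal break frequency, and a reader of 1.3.1 would think the matter had been dealt with.

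**Working it through.** **1. The plan's own figure.** Section 1.3.1 gives 0.63 ± 0.16 (SD) against 0.39 ± 0.23 (controls) and concludes that 15 per group give 80% power at two-sided 0.025.

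- Pooled s.d. = √((0.16² + 0.23²)/2) = 0.198; standardised difference = 0.24/0.198 = 1.21.
- The exact t-test gives power of 79.0% at 14 per group, 82.3% at 15 and 92.8% at the 20 to be recruited.

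The stated 15 reproduces. The present point does not affect it.

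**2. Is the adjustment made anywhere else in the fMRI plan?**

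| Place | What it contains | Adjusts SD vs. SD/VT for voice? |
|---|---|---|
| 1.3.1, subject-level regression | task, drift and motion regressors | No |
| 1.3.1, voice variables | within-group analysis | Not as written |
| 1.3.1, ANOVA | subject, task, group | No |
| 1.3.1, PPI and DCM group comparisons | no voice covariate listed | No |
| 1.3 matching | alcohol effect, age, gender, SD type | No |
| 1.3.4 symptom correlations | computed in each patient group | No |
| 1.3.2 gray matter tests | voice breaks and tremor as nuisance effects | Yes, but for structure only |

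**3. Does a within-group covariate change the contrast?** That depends on centring and on whether the covariate reaches the contrast. A simulation used 20 per group, no direct group effect, and activation related to breaks with the same slope in both groups.

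- Covariate centred within each group: the mean difference equals the unadjusted one. For a gap of 0.5 s.d. and a correlation of 0.5 it is 0.247 s.d. either way.
- Covariate centred over both groups, in the between-group model: the spurious difference is about 0 and rejection is 2.2% to 2.8% against a nominal 2.5%.
- Separate slopes per group with common centring: again about 0.

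Section 1.3.1 states no centring and does not say that the variables enter the contrast.

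**4. Illustration of size.** The documents give neither the between-group gap in breaks (g, in s.d. units) nor the within-group correlation of breaks with signal (r), so both are assumed. With activation scaled to unit within-group s.d., the difference produced through breaks alone is d = g × r. With n = 20 per group, df = 38 and noncentrality = d × √(20/2) = 3.162 × d. The two-sided critical values of t are 2.334 at 0.025 and 2.980 at 0.005.

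| g | r | d | Noncentrality | Significant at 0.025 | Significant at 0.005 |
|---|---|---|---|---|---|
| 0.25 | 0.3 | 0.075 | 0.237 | 2.9% | 0.6% |
| 0.5 | 0.5 | 0.25 | 0.791 | 7.1% | 2.0% |
| 0.75 | 0.7 | 0.525 | 1.660 | 26.3% | 10.9% |
| 1 | 0.7 | 0.7 | 2.214 | 46.0% | 24.0% |

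The 0.005 column is shown because 1.3.1 uses that voxelwise threshold together with a minimum cluster size. Neither column includes a cluster rule or whole-brain correction.

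**5. Why tremor is different.** Tremor defines SD/VT and should be near zero in SD. If SD tremor is set to zero and the SD/VT mean lies 1, 2 or 3 s.d. above zero (assumed), the variance of the group effect is inflated about 1.9, 3.5 or 6.3 times when tremor is added. Adjustment could also remove the effect under study.

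**The case against.** **Within-group may be loose wording.** The sentence stands in the subject-level paragraph, before the group analysis begins, and the section refers to a pipeline from earlier papers. If voice measures entered before the group maps were formed, the estimates carried forward could be partly adjusted. This stands as an ambiguity. It does not repair the text, which says within-group and lists no such regressor.

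**A reader might infer that a within-group covariate can never adjust a group contrast.** That is too strong. Step 3 of the working shows that common centring, carried into the contrast, removes the spurious difference. What the documents support is narrower: the plan does not say that the variables enter the contrast, and the model it gives omits them.

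**A reader might infer that break-related differences are false positives.** The documents do not support this. Voice breaks are a core symptom, the tasks are chosen to elicit symptoms, and 1.3.4 looks for abnormalities that correlate with symptoms. Activation that differs because one group breaks more may be part of the disorder. Whether distinct means net of break frequency is a choice that the plan leaves unstated.

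**A reader might take the percentages as error rates of the maps.** They are not. They concern one voxel without correction, on assumed inputs, and nothing in the documents says that the two groups differ in break count. With no gap there is no bias from breaks.

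**The correlations in 1.3.4 help.** They show which regions track severity within each group. This aids interpretation but does not adjust the contrast.

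**Conclusion.** The mismatch between purpose and method is on the page, and nothing else in the fMRI plan resolves it. As written, the SD vs. SD/VT contrast is not adjusted for voice breaks or tremor, while the text tells the reader that these differences are accounted for. The consequence is conditional: if break frequency during scanning differs between the groups and relates to activation, some distinct regions cannot be separated from break frequency. How large this is cannot be found from the documents. The illustrative ranges, about 3% to 46% at uncorrected 0.025 and 0.6% to 24% at 0.005, rest on the assumed gaps and correlations and on a single voxel. The point limits what the distinct maps can be said to show; it does not establish that any of them is an artefact. It should be settled before analysis, and it leaves the sample size untouched.

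**What to change.** 1. Keep the unadjusted SD vs. SD/VT contrast as the main result.
2. Add a prespecified supporting run of the same contrast with in-scanner voice-break count as a covariate, centred over both patient groups together. Leave tremor severity out, because it defines SD/VT.
3. Mark which distinct regions survive, and describe the others as not separable from voice-break frequency.
4. Reword the sentence in 1.3.1 so that it no longer says the within-group variables account for differences between the groups. State that tremor-related differences in performance remain in the contrast.
5. While editing, correct the source given for the symptom measures: 1.3.1 points to Study 1.3.3, the diffusion study, whereas the acoustic severity scores are described in 1.3.4.

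The cost is one extra model, one degree of freedom, and some loss of precision if breaks differ by group. No further patients or scans are needed: 1.3.4 already provides for voice recording during scanning and blinded scoring of breaks.
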